#### 9.1.4. Prior to Discharge (Post RF Ablation)

Worst pain score at the treated site will be collected prior to discharge or within 12 hours of the procedure. Collection of post-treatment images (e.g., MRI, PET, etc.) at the treated site(s) (if available) in the US and CAN only. During this time, reportable adverse events, device deficiencies and deviations will also be collected.

#### 9.1.5. Clinic Visits (3 days, 1 week, 1-, 3-, 6-, and 12-months post RF ablation)

Clinic visits will be scheduled 3 days, 1 week, 1-, 3-, 6-, and 12-months post RF ablation. The following information will be collected at these visits:

- Concomitant cancer and/or tumor treatments relevant to the treated site(s), if applicable (refer to section 9.6.5
- Concomitant pain medications (refer to section 9.6.6)

#MDT16075 Version 4.0

Page 33 of 81 Medtronic

- BPI includes worst pain score at the target treatment site in the past 24 hours (refer to section 9.6.1)
- PI assessment of local tumor control optional
- EQ-5D-5L (refer to section 9.7.9)
- EORTC QLQ-C15-PAL (not applicable for subjects with benign bone tumors) (refer to section 9.7.10)
- Reportable adverse events/device deficiencies/deviations (refer to section 11 and section 9.10)
- Collection of post-treatment images (e.g., MRI, PET, etc.) at the treated site(s) (if available) US and CAN only (refer to section 9.6.8)

Every attempt should be made to complete the required onsite clinic visit. However, if a subject is unable to complete an onsite visit, a phone follow-up visit eCRF can be completed by the Investigator/RC to obtain the required data elements.

Unscheduled visits will only be collected for visits conducted in the context of the study. The events required by each visit are presented in Table 9-1.

#MDT16075 Version 4.0

Page 34 of 81

Medtronic

#### **Table 9-1: Schedule of Events**

Events	Enrollment Baseline 	OsteoCool Procedure (Day 0) 	Prior to Discharge or within 12 hours of the procedure	3 days, 1 week, 1- ,3-,6-, and 12- Month Visits & unscheduled visits 	Phone eCRF (if needed)
Informed Consent Form 	Х				
Eligibility (Inclusion/Exclusion Criteria)	Х				
Pregnancy Test (Women of child-bearing potential)	X				
Demographics and Disease Characteristics	Х				
Karnofsky Performance Scale 	X 				
OsteoCool / procedure details		Х			
	Х	Х	х	Х	Х
Generator data uploads (if available)		Х			
PI assessment of local tumor control (optional)		х		х	
Concomitant cancer and/or tumor treatments, relevant to the target site(s)	х	Х		Х	Х
Concomitant pain medications 	Х	Х		Х	Х
Worst pain score only			Х		
BPI (Short Form) – includes worst pain score in the past 24 hours	Х			х	Х
EQ-5D-5L	х			Х	Х
EORTC-QLQ-C15-PAL 	X 			X 	
Deviations	Х	Х	X	X	Х
Event Review (AE/DD)	Х	Х	Х	X	Х

- 1) Informed consent must be obtained prior to performing any study-specific procedures.
- 2) Baseline Visit, Enrollment Visit and procedure can occur on the same day. Baseline visit shall be performed ≤ 21 days before the OsteoCool procedure
- 3) Oral narcotics within past 24 hours
- 4) Not applicable for subjects with benign bone tumors
- 5) Unscheduled visits will only be collected for visits conducted in the context of the study

Page 35 of 81

Table 9-2: Protocol Visit Windows\*

Visit	Visit ranges		
Enrollment/Baseline	NA		
Procedure (Day 0)	≤21 days after Baseline visit		
Discharge	Prior to hospital discharge or within 12 hours of the procedure		
Monthly Clinic Visits	3 Days: 3 days ± 2 Days after Day 0 1 week: 7 days± 2 Days after Day 0 1-Month Visit: 30 days ± 15 Days after Day 0 3-Month Visit: 90 days ±30 days after Day 0 6 Month Visit: 180 days ±59 days after Day 0 12 Month Visit: 365 days ± 90 days after Day 0		

\*Every attempt should be made to complete the required onsite clinic visit. However, if a subject is unable to complete an onsite follow-up visit due to physical circumstances, a Phone follow-up visit eCRF can be completed by the Investigator/RC to obtain the required data elements.

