### 9.7. Assessment of Quality of Life Measures

Subjects and/or Principal Investigator or qualified (delegated) designee (if completed by phone) will complete the study questionnaires confidentially on paper forms and this data will be entered into the OC RDC system by site personnel. The patient can consult with the site for direction on how to complete the questionnaires. Questionnaires should be completed prior to the meeting with the investigator. Site personnel should review all forms for completeness.

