### 9.7.9. European Quality of Life – Five Dimensions (EQ-5D-5L)

The European Quality of Life – Five Dimensions (EQ-5D), version 5L, is a standardized measure of health status developed by the EuroQol Group and a widely used validated tool to determine health-related quality of life. The EQ-5D-5L consists of two sections, the descriptive system and the EQ visual analogue scale (EQ VAS).

The EQ-5D descriptive system consists of 5 dimensions: mobility, self-care, usual activities, pain/discomfort, and anxiety/depression. Each dimension has 5 levels of severity: no problems, slight problems, moderate problems, severe problems, extreme problems. The subjects are asked to indicate his/her health state by selecting the most appropriate statement in each of the 5 dimensions.

The EQ VAS records the respondent's self-rated health on a 20 cm vertical, visual analogue scale with endpoints labelled 'the best health you can imagine' and 'the worst health you can imagine'. This information can be used as a quantitative measure of health as judged by the individual respondents.

The EQ-5D can be completed by the subject, in-person interview, or by phone interview by the Principal Investigator or qualified (delegated) designee.

#### 9.7.10. European Organization for Research and Treatment (EORTC QLQ-C15-PAL) 35

The EORTC QLQ-C15-PAL is a module developed to measure the QOL in patients with bone metastases. It includes four subscales: painful sites, pain characteristics, functional interference, and psychosocial aspects. This questionnaire is not applicable for subjects with benign bone tumors.

The EORTC QLQ-C15-PAL must be completed by the subject.

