#### 9.9. Recording Data

The Investigator must ensure accuracy, completeness and timeliness of the data reported in the eCRFs and in all other required reports. Data reported on the eCRFs must be consistent with the source documents, and discrepancies need to be justified in a documented rationale, signed and dated by the Investigator, and filed in the subject medical file or appropriate location.

#MDT16075 Version 4.0 Page 40 of 81

All source data entered in the eCRFs should be located in the subject's medical records/source document (electronic or paper), (e.g., hospital records, surgery reports, x-rays, MRIs, CTs, or any other material that contains original information used for data collection including the documentation of AEs and study source document completed by the Investigator or site staff). Subject completed questionnaires as well as data collected during subject phone calls will be considered as source data.

This study will be conducted using a remote data capture system. The Oracle Clinical Remote Data Capture (RDC) system allows the study centers to enter study data into the sponsor's database over a secure internet connection. Required data will be taken from source documents and directly entered into the study database by authorized site personnel in accordance with applicable regulations.

If the subject is unable to return to the investigational site for their scheduled clinic visit, the study site can contact the subject and collect the following data by phone using the phone visit source document worksheet:

- BPI conducted by phone
- EQ-5D-5L phone version
- Oral narcotic intake in the past 24 hours
- Concomitant procedures/treatments
- Reportable adverse events and/or device deficiencies

The Principal or Sub-Investigator, or an individual delegated by the Principal Investigator on the Delegation of Authority and Signature Form, is responsible for documenting and entering data for the study on the eCRFs. The Principal Investigator or delegated Sub-Investigator is required to approve all data on CRFs via electronic signature.

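### Follow-up EORTC QLQ-C15-PAL is planned only for subjects seen in person, while BPI and EQ-5D-5L are also collected by phone

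*Combined protocol and SAP*

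**What the plan says.** Protocol section 9.1.5, Table 9-1 and the SAP's Figure 5-1 place the EORTC QLQ-C15-PAL at every follow-up visit for subjects with metastatic disease. Benign-tumor subjects are exempt.

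On when a phone contact may replace a visit, the protocol has three wordings:
- Table 9-2, footnote: "if a subject is unable to complete an onsite follow-up visit due to physical circumstances, a Phone follow-up visit eCRF can be completed".
- Section 9.1.5: "if a subject is unable to complete an onsite visit, a phone follow-up visit eCRF can be completed by the Investigator/RC", with no reason required.
- Section 9.9, for a subject who cannot return to the site: "the study site can contact the subject and collect the following data by phone using the phone visit source document worksheet". The list that follows includes the BPI and the "EQ-5D-5L phone version", but not the EORTC form.

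On how each questionnaire may be completed:
- Section 9.7.9: "The EQ-5D can be completed by the subject, in-person interview, or by phone interview". Section 9.6.1 gives the BPI the same choice.
- Section 9.7.10: "The EORTC QLQ-C15-PAL must be completed by the subject".
- Section 9.7, the general introduction: "Subjects and/or Principal Investigator or qualified (delegated) designee (if completed by phone) will complete the study questionnaires confidentially on paper forms", with no exception for the EORTC form.

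**The concern.** Section 9.1.5 counts the EORTC form among the information due at each follow-up and offers the phone contact as the way to obtain what is due when the subject cannot attend. For this form the phone contact cannot do that: no phone mode is allowed and no way of sending the form to the subject is described.

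One stated reason for a phone contact is the subject's physical state, which a palliative-care quality-of-life questionnaire is meant to reflect. Metastatic subjects may enter with a Karnofsky score as low as 40, and section 13.1.4 names death and deteriorating health as the expected main causes of missing endpoint data. If phone subjects have fared worse than those who attend, EORTC results after baseline will flatter the outcome. They will also describe fewer and different people from the BPI and EQ-5D-5L at the same time point, so the measures cannot be read side by side without care. Forms not collected at the time cannot be recovered later.

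**Working it through.** **1. Is the omission real?** The relevant places, side by side:

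| Place | BPI | EQ-5D-5L | EORTC QLQ-C15-PAL |
|---|---|---|---|
| Table 9-1, clinic and unscheduled visits | marked | marked | marked (metastatic only) |
| Table 9-1, phone column | marked | marked | blank |
| Section 9.9, phone list | listed | listed | not listed |
| Sections 9.6.1, 9.7.9, 9.7.10 | subject, or interview in person or by phone | subject, or interview in person or by phone | subject only |

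The blank cell is not an accident of table layout, because the list in section 9.9 omits the form too. Follow-up EORTC data are therefore planned only from subjects seen in person.

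**2. The plan's own computed figure.** The only computed sample size concerns BPI worst pain. A one-sample two-sided t-test with difference 2, SD 3.5 and alpha 0.05 has power 0.899 at n = 34 and 0.907 at n = 35, so 35 is reproduced. Allowing for 32% loss, 35 / 0.68 = 51.5, rounded up to 52. Neither figure is touched, because the BPI is collected by phone and section 13.1.4 allows phone calls for the primary endpoint.

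**3. Form of the bias.** Let p be the share of assessed subjects reached by phone, and let C_on and C_ph be the mean change from baseline in on-site and phone subjects, scored so that higher is better.
- Mean change in all assessed subjects: (1 - p) x C_on + p x C_ph.
- Mean change observed: C_on.
- Bias: C_on - [(1 - p) x C_on + p x C_ph] = p x (C_on - C_ph).

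What matters is the difference in change, not in level. If phone subjects already scored lower at baseline and then changed by the same amount, the bias in mean change is zero. If unpaired visit means were reported instead, the gap in level would apply.

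**4. Size.** The documents give no phone share, no EORTC standard deviation and no difference in change. As an illustration only, with assumed p of 5% to 30% and an assumed difference in change of 0.5 to 1.0 SD:

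| p | bias at 0.5 SD | bias at 1.0 SD |
|---|---|---|
| 5% | 0.025 SD | 0.05 SD |
| 10% | 0.05 SD | 0.10 SD |
| 20% | 0.10 SD | 0.20 SD |
| 30% | 0.15 SD | 0.30 SD |

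**5. Different denominators.** The enrollment goals in section 13.1.1 give 100 + 100 = 200 metastatic subjects. Assume all are treated and that 68% supply 3-month data, as in the earlier study used for the sample size: 200 x 0.68 = 136 with BPI. With EORTC, 136 x (1 - p) gives 129, 122, 109 and 95 for p of 5, 10, 20 and 30%, which is 65% down to 48% of the 200.

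**The case against.** Self-completion is a deliberate choice of mode, and the specific provisions (section 9.7.10, section 9.9 and Table 9-1) agree with each other. Section 9.7 is a general introduction, so its conflict with them is mainly a matter of wording. This stands, but self-completion excludes an interviewer, not a form completed at home.

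Sites must try to secure the on-site visit. The windows at 3, 6 and 12 months are wide (±30, ±59 and ±90 days), and the form is also marked for unscheduled visits. This will keep the phone share down by an unknown amount. It helps little at 3 days and 1 week, where the window is ±2 days.

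No hypothesis test is attached to the additional measures, and the EQ-5D-5L still captures quality of life by phone. Both are true, and they limit the importance of the point.

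Four stronger readings are tempting and are not supported:
- *Phone visits are reserved for the physically unfit, so missingness is caused by the state being measured.* Only the Table 9-2 footnote names a physical reason. Sections 9.1.5 and 9.9 admit any inability to attend, so some missing forms will be unrelated to health.
- *The 32% loss indicates how common phone visits will be.* It is the share without a 3-month pain score in an earlier study. Here a phone subject would supply a pain score and so would not be in that group.
- *The bias can be stated in score points.* That needs an assumed phone share, an assumed deficit and a scoring range the documents do not give. A deficit in level would also not measure bias in change.
- *The SAP has no method for missing EORTC data.* The text on the additional measures is not available in the public documents, so this cannot be said.

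**Conclusion.** The point holds in a limited form. Collection of the EORTC form after baseline depends on attendance in person, and the other two questionnaires do not share that restriction. That is certain from the text. It is a reasonable inference, not a demonstrated fact, that some of the missing forms will come from sicker subjects and that post-baseline results will look somewhat better than they are. The inference rests on the physical reason in the Table 9-2 footnote and on the study population. The size of the bias is unknown: the 0.025 to 0.30 SD above rests entirely on assumed inputs, and the bias in change could be nil. Baseline EORTC scores, the primary and secondary pain endpoints and the sample size of 35 and 52 are unaffected. This is a cheap improvement to a supporting measure.

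**What to change.** In sections 9.7.10 and 9.9 and the phone column of Table 9-1, add a remote route in which the subject still completes the form:
- **1-, 3-, 6- and 12-month visits:** mail or e-mail the form, for return by mail, fax or secure e-mail within the window. Section 9.3 already allows such routes for consent amendments, and section 9.7 already uses paper forms.
- **3-day and 1-week visits:** hand over the form at discharge or e-mail it. The subject completes and dates it within the window, and later return is accepted, since postal return does not fit ±2 days.

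Bring the general wording of section 9.7 into line with section 9.7.10, and reconcile the Table 9-2 footnote with sections 9.1.5 and 9.9 on when a phone contact is allowed. Record the mode of each visit and the reason for a phone contact. Report EORTC completion by visit and mode beside the scores. Because BPI and EQ-5D-5L come from both modes, comparing them by mode would show how far phone subjects differ.

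The cost is a protocol wording change, postage or e-mail of one form, and tracking of returns at about 20 sites. No new visit or assessor is needed. Some forms will come back late or not at all, and non-return may itself depend on illness, so the bias is reduced rather than removed.

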### 9.2. Subject Screening

Subjects may be recruited through the investigator's practice and referring physicians.

Potential subjects may be identified through chart reviews or as new or existing patients. If subjects are recruited from outside the investigator's practice, sites are to ensure that appropriate release for access to the subject's records (paper and/or electronic) is obtained. Any subject recruitment materials disseminated to subjects (advertisements, handouts, posters, and social media) must be approved by the IRB/EC prior to use.

Recruited subjects will be screened by the Principal Investigator or authorized site personnel by reviewing the study's inclusion and exclusion criteria. All subjects must be consented in accordance with the protocol prior to any study-specific procedures.

A screening log will be completed by the site to maintain a cumulative log of all screened subjects with reason for screening failure when applicable and provided to Medtronic upon request.

The Investigator will maintain a listing of all subjects enrolled in the clinical investigation and a subject identification code linked to each subject's name.

## 9.3. Subject Consent

The informed consent process will be performed in accordance with the ethical principles that have their origin in the Declaration of Helsinki and 21 Code of Federal Regulations (CFR)§50 Protection of Human Subjects (US only).

Prior to entering the study, the Principal Investigator or delegated designee will explain to each subject the purpose and nature of the study, procedures, expected study duration, available alternative therapies, and the benefits and risks involved with study participation and the potential treatment. Subjects will be given a copy of the IRB/EC-approved IC and will have time to review the document and

to ask questions and will be informed of their right to withdraw from the study at any time without prejudice; ICs will be provided in a language understandable to the subject. After this explanation and before any study-specific procedures have been performed, the subject will voluntarily sign and date the IC. In Europe, the PI or delegate must also sign the IC. Prior to participation in the study, the subject will receive a copy of the signed and dated informed consent and any other written information provided to the subject.

The Principal Investigator or qualified (delegated) designee will document the informed consent process, including the date of consent and name of the person conducting the consent process in the subject's medical record. If the Baseline visit, Enrollment Visit and procedure are done on the same day, documentation should indicate that the IC was signed before any study related procedures. A copy of the signed IC will also be placed in the subject's medical record.

Amendments to the IC can be obtained by other methods if the subject is unable to return due to illness or logistics. The IC should be sent to the subject by mail, fax, or email and then a discussion should occur by phone. The subject must be able to refer to the written document during the phone discussion. The subject can sign/date the IC and return it by mail, fax, scanning/emailing through a secure account, or posting it to a secure internet address. Alternatively, the subject may bring the signed and dated consent form to his/her next visit to the clinical site or mail it to the clinical investigator. The subject must receive a copy of the consent form. This process should be documented in the subject's medical record.

### 9.4. Randomization and Treatment Assignment

Randomization is not applicable for this study.

### 9.5. Medication Compliance

Medication compliance is not applicable for this study.

# 9.6. Assessment of Efficacy

### 9.6.1. Brief Pain Inventory (BPI)

The Brief Pain Inventory short form is a 9 item self-administered questionnaire used to evaluate the severity of a patient's pain and the impact of this pain on the patient's daily functioning. The patient is asked to rate their worst, least, average, and current pain intensity, list current treatments and their perceived effectiveness, and rate the degree that pain interferes with general activity, mood, walking ability, normal work, relations with other persons, sleep, and enjoyment of life on a 11 point scale.

The worst pain question in the BPI will be used to evaluate the pain severity:

Please rate your pain by circling the one number that best describes your pain at its worst in the last 24 hours (circle only one number, 0-10). No pain = 0, Pain as bad as you can imagine = 10

The BPI pain interference is typically scored as the mean of the seven interference items (general activity, mood, walking ability, normal work, relations with other people, sleeping, and enjoyment of life). The mean can be used if more than 50% or 4/7 of the total items has been completed.

The general pain question (Question #1), pain map (Question #2) and the medication question (Question #7) will not be used in this study. The removal of these questions does not affect the validity of the questionnaire and was approved by the BPI author [name], PHD

The BPI can be completed by the subject, by in-person interview or by phone interview by the Principal Investigator or qualified (delegated) designee.

### 9.6.2. Cancer Medical History and Demographics

Relevant cancer medical history and demographic information will be collected at the Baseline visit and reported on the applicable eCRFs.

### 9.6.3. Karnofsky Performance Scale (KPS)

The Karnofsky Performance Scale Index classifies patients as to their functional impairment. This can be used to compare effectiveness of different therapies and to assess the prognosis in individual patients. Functional status is assessed by the physician. The KPS ranges from 100 to 0, where 100 is "perfect" health and 0 is death. The lower the Karnofsky score, the worse the survival prognosis for most serious illnesses.

Not applicable for subjects with benign bone tumors.

#### 9.6.4. Disease Characteristics

- Primary cancer type and year of diagnosis
- Histology (if available)
- Metastases and/or tumor site information location, characteristics
- Imaging (if available), for US and CAN subject/sites only

#### 9.6.5. Prior and Concomitant Cancer and/or Tumor Treatments

Most recent treatments relevant to the treated/target site(s):

- Chemotherapy
- Radiation therapy
- Immunotherapy
- Antibody therapy
- Surgical procedures for cancer and/or tumor treatment including other ablative therapies
- Other, specify

#MDT16075 Version 4.0 Page 38 of 81

#### 9.6.6. Prior and Concomitant Medications

There are no restrictions to prior or concomitant medications before or during the study. The specific concomitant medications listed below should be documented as concomitant medications and will be updated at each visit:

- **Osteoporosis medication(s):** Antiresorptive medications (e.g., bisphosphonates, parathyroid hormone (PTH), calcitonin), calcium, and vitamin D.
- **Steroid(s):** any steroid use, including steroid inhalers
- **Oral narcotics in last 24 hours.** This information will be converted to oral morphine equivalent dose (OMED) (including transdermal patches)

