### 9.6.7. Response Rate

Response rate at 3 months post RF ablation is defined in Table 9-3. Complete Response (CR) and Partial Response (PR) will be considered as treatment response. Pain Progression (PP) and Indeterminate Response (IR) will be considered as treatment non-response.

T	able	9-3:	Co	mposite Er	ndpoint
,	_				4.1

ient nse	Complete Response (CR)	A worst pain score of 0 with no concomitant increase in daily oral morphine equivalent dose (OMED) within the last 24 hours
Treatment Response	Partial Response (PR)	Pain reduction of 2 or more on a scale of 0-10 without increase in OMED, or OMED reduction of 25% in the last 24 hours or more from baseline without an increase in pain.
Treatment Non- response	Pain Progression (PP)	Increase in pain score of 2 or more above baseline worst pain score with stable OMED, or an increase of 25% or more in OMED within the last 24 hours compared with baseline with the worst pain score stable or 1 point above baseline.
Treat	Indeterminate Response (IR)	Any response that is not captured by the complete response, partial response, or pain progression definitions

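### The visible plan records opioids by mouth (and, in one section, by patch) but by no other route, so moving dose to an unrecorded route can be scored as Partial Response in Table 9-3

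*Combined protocol and SAP*

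**What the plan says.** Three places in the protocol describe the opioid data.

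- Section 9.6.6 lists three classes of concomitant medication to document: osteoporosis drugs, steroids and oral narcotics in the last 24 hours. Of the narcotics it says "This information will be converted to oral morphine equivalent dose (OMED) (including transdermal patches", and the list "will be updated at each visit".
- Table 9-1, footnote 3, attached to the pain-medication row, reads "Oral narcotics within past 24 hours". The row is ticked for baseline, procedure, follow-up and phone.
- Section 9.9, in the list of data that may be taken by phone, reads "Oral narcotic intake in the past 24 hours".

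Section 9.6.1 drops the medication question from the BPI, so the questionnaire gives no second source.

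Section 9.6.7 and Table 9-3 use OMED in every named category. Complete Response is a worst pain score of 0 with no OMED increase. Partial Response has two alternative limbs. The pain limb is "Pain reduction of 2 or more on a scale of 0-10 without increase in OMED". The opioid limb, which is sufficient alone, is "OMED reduction of 25% in the last 24 hours or more from baseline without an increase in pain". Pain Progression also has two limbs. The first is "Increase in pain score of 2 or more above baseline worst pain score with stable OMED". The second is an OMED rise of at least 25% "compared with baseline with the worst pain score stable or 1 point above baseline". Everything else is Indeterminate. The first two categories are response and the last two are non-response.

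Protocol 13.1.4 and SAP 7.5 attach no hypothesis test to the additional measures.

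**The concern.** A composite of pain and opioid use works only if the opioid half measures total opioid exposure. Here the recorded quantity is dose by mouth, with patches in one section and without them in two. A subject who goes from tablets to an infusion has a recorded OMED of zero, and Table 9-3 cannot tell this from stopping opioids. Some loss of the oral route is plausible in advanced cancer, and 9.6.6 places no restriction on medications.

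This composite is the only visible measure that combines pain with opioid use. The study has one arm, so no comparator would carry the same error and offset it. What is at stake is the reported 3-month response rate, which may be read as evidence of pain relief net of analgesics.

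**Working it through.** **Figure to reproduce.** The documents state no response rate, sample size or power for Table 9-3. The 35 completers in protocol 13.3.5 and SAP 6 belong to the t-test on worst pain, whose change score (protocol 13.3.4) contains no OMED term. The check is therefore of the classification logic.

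**Inputs.** The rules are those of Table 9-3. The subject is illustrative: baseline pain 6, baseline opioid 60 mg OMED, all by mouth. The visible text does not define stable OMED, so it was read both as within 25% of baseline and as exactly unchanged. CR, PR, PP and IR are the four categories.

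**Step 1: whole dose moved to an unrecorded route.** Recorded OMED goes from 60 to 0, a change of (0 − 60)/60 = −100%. The true dose is either unchanged (60) or raised to 90, which is (90 − 60)/60 = +50%.

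| Pain change | Class as recorded | All routes counted, true dose 60 | All routes counted, true dose 90 |
|---|---|---|---|
| −2 | PR | PR | IR |
| −1 | PR | IR | IR |
| 0 | PR | IR | PP |
| +1 | IR | IR | PP |
| +2 | IR | PP | IR |

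Both readings of stable give this table. Responder status is wrong in 5 of the 10 comparisons, always towards response. It is not wrong when pain rises, or when pain falls by 2 with the true dose unchanged.

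**Step 2: how much dose must move.** With pain unchanged, moving 15 of 60 mg gives (45 − 60)/60 = −25%, hence PR. Moving 12 of 60 mg gives (48 − 60)/60 = −20%, hence IR. A quarter of the dose is enough.

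**Step 3: the other response limbs.** The row for −2 with true dose 90 shows the pain limb of PR met only because the rise was not recorded. Likewise, pain 6 to 0 with a true rise to 90 is CR as recorded and IR with all routes counted.

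**Step 4: patches.** Under 9.6.6 a switch to a patch is counted and causes no error. Under the wording of footnote 3 or 9.9 a patch behaves like the unrecorded route in step 1. If one wording governs at baseline and the other at 3 months, a continuing patch user shows a false change.

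**Step 5: the reverse move.** Take 60 mg by an unrecorded route at baseline and 30 mg by mouth at 3 months, with pain down 2. Recorded OMED rises from 0 to 30, so the class is IR; with all routes counted it is PR. This error runs against response.

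**Step 6: worse on both measures.** Pain +2, +3 or +4 combined with OMED +25%, +50% or +100% is IR in all 9 cells, under either reading of stable. The pain limb of PP fails because OMED is not stable, and the opioid limb fails because pain is more than 1 point up. Pain +1 with the same three OMED rises is PP in all 3 cells. PP and IR are both non-response, so CR + PR does not change.

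**Scale.** If the denominator were the 35 completers (an assumption; the visible text does not give one), each false responder would add 1/35 = 2.9 percentage points.

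**The case against.** The best reply is that 9.6.6 governs. It includes patches and applies at each visit, the visit lists in 9.1.2, 9.1.3 and 9.1.5 refer to it, and footnote 3 and the 9.9 entry can be read as shorthand for it. This stands in part. A reader might infer that capture is oral only throughout, and that any switch to a non-oral opioid counts as response; the patch wording in 9.6.6 rules that out. A reader might also infer that clinic and phone visits collect different data. The documents show a mismatch between sections: Table 9-1 uses one row and one footnote for both visit types, and the phone worksheet is not in the public file.

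A second reply is that the Additional Measures text (protocol 5.1.3, 5.2.3 and 13.6; SAP 4.3 and 7.9.3) is missing from the public copy, and that the SAP reference list includes an opioid resource. Conversion factors and a definition of stable OMED may be there, and I do not count their absence against the plan. But a derivation rule cannot restore doses that were never recorded, and the collection sections are visible.

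A third reply is that the progression gap has no effect on the response rate. That is correct. No visible output reports progression separately, so the documents do not support a statement that a reported progression rate is understated. The category definitions are also attributed to a published consensus, and departing from them has a cost in comparability.

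**Conclusion.** The point holds for opioid capture. The three passages disagree about patches, no visible passage records other non-oral routes, and Table 9-3 read literally then makes some subjects responders through a change of route or an unrecorded dose rise. For dose moving off the recorded routes, every error in responder status is towards response. A net bias in that direction assumes that such moves outnumber the reverse move in step 5.

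The size is unknown. It is tempting to take it from the acetabular series in protocol 4.4, where 3 of 12 patients went to hospice within a week. Those patients say little about 3-month completers in this study, and the series reports nothing on opioid routes. It is also tempting to count every route switch as one false responder; step 1 shows that many are not. The 2.9 points is a per-subject scale and not an estimate of bias.

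The consequence is limited to a descriptive measure; the primary test is unaffected. The progression gap in step 6 is a minor point that changes only the split between PP and IR. Confidence is high in the logic and low in the magnitude.

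**What to change.** 1. Reconcile 9.6.6, Table 9-1 footnote 3 and the phone list in 9.9, so that all opioids by any route in the past 24 hours are recorded and converted to OMED in the same way at every visit, including phone visits.
2. For data already collected without other routes, report the Table 9-3 response rate with a sensitivity rate that does not count PR met on the OMED limb alone. This does not repair step 3, where an unrecorded rise passes the no-increase condition; say so in the report. A retrospective correction from the medication record is not dependable, because 9.6.6 does not ask for these drugs.
3. If PP is tabulated separately, show Table 9-3 as written beside a version that counts pain up 2 or more with OMED up 25% or more as progression. The first keeps comparability with the cited consensus.

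The cost is a wording change to the CRF and phone worksheet and a few lines of derivation. The response rate may come out slightly less favourable, and the sensitivity rate will also drop subjects who truly reduced their opioids without a 2-point fall in pain.
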